6.1.1 Participant identification

Service-user participants will be identified by a clinician responsible for their care in a perinatal community mental health service, who will refer them to the research based either on the clinician's clinical judgment that they meet eligibility criteria. The clinician will make a judgement on the inclusion and exclusion criteria. Clinicians will obtain verbal permission from mothers to pass their details to the research team and these will be emailed to the researchers over NHS-mail to NHS-mail encrypted server. This verbal consent will be recorded in the potential participant's medical records. The researchers will then confirm that the participant meets eligibility criteria.

Only a member of the patient's existing clinical care team will have access to patient records in order to identify eligible participants.

Clinician participants will be approached directly by the research team.

6.2 Consent

The Principal Investigator (PI) will retain overall responsibility for the informed consent of participants at their site and will ensure that any person delegated responsibility to participate in the informed consent process is duly authorised, trained and competent to participate according to the ethically approved protocol, principles of Good Clinical Practice (GCP) and Declaration of Helsinki.

Informed consent will be obtained prior to any participant undergoing procedures that are specifically for the purposes of the trial and are out-with standard routine care at the participating site, including the collection of identifiable participant data.

The right of a participant to refuse participation without giving reasons will be respected.

The participant will remain free to withdraw at any time from the trial without giving reasons and without prejudicing his/her further treatment and will be provided with a contact point where he/she may obtain further information about the trial.

The PI takes responsibility for ensuring that all vulnerable subjects are protected and participate voluntarily in an environment free from coercion or undue influence

- During the informed consent process, the potential participant and a member of the research team will discuss the nature and objectives of the trial and possible risks associated with their participation
- The potential participant will be presented with a written information sheet and will be asked
 to give written informed consent using documents approved by the REC and in compliance
 with GCP, local regulatory requirements and legal requirements.
- Potential participants will have the opportunity to ask questions
- The researchers taking consent will be trained in assessing the capacity of the person to consent to taking part, i.e. if the potential participant is able to:
 - o understand the purpose and nature of the research
 - understand what the research involves, its benefits (or lack of benefits), risks and burdens
 - understand the alternatives to taking part
 - o retain the information long enough to make an informed decision.

BOOST-2 Boosting Baby Communication & Play

- o make a free choice
- o make this particular decision at the time it needs to be made
- o understand how their interests will be protected

Potential participants will be assumed to have the mental capacity to make a decision unless it is shown to be absent. Those deemed to lack capacity to consent will be ineligible for study participation.

6.4 Baseline data

- 1) Sociodemographics and treatment history interview. Brief interview to record participants' age, gender, ethnicity, employment status and type, educational level, relationship status, number and age of children, years in contact with mental health services, risk history, lifetime history of psychiatric inpatient admissions, lifetime history of A&E admissions for mental health reasons, perinatal mental health and childrens' social services referrals. This information, in addition to current primary psychiatric diagnosis, will also be recorded from patients' clinical records where available.
- 2) Parental emotion dysregulation. This will be assessed using the Difficulties in Emotion Regulation Scale (DERS-16) (Gratz and Roemer, 2004, Bjureberg et al., 2016), a 16-item self-report measure. The measure demonstrates high internal consistency, good test–retest reliability, and adequate construct and predictive validity (Gratz and Roemer, 2004, Bjureberg et al., 2016).
- 3) Parental borderline personality traits. This will be assessed as an indicator of complex emotional needs linked to emotional dysregulation, using the McLean Screening Instrument for Borderline Personality Disorder. A cut-off of 7 identifies the presence of borderline personality traits with a sensitivity of .90 and specificity of .93 (Zanarini et al. 2003).
- 4) Parenting Stress. This will be measured using the Parental Stress Scale. This is an 18 item self-report scale assessing positive and negative experiences of parenthood. The measure has demonstrated good internal consistency and test-retest reliability, as well as convergent validity with measures of emotional distress and parenting satisfaction (Berry & Jones 1995).
- 5) Parental self-efficacy. This will be measured using the Karitane Parenting Confidence Scale. This is a 15- item self-report scale assessing mothers' perceived self-efficacy in caring for their child. The measure has demonstrated good internal consistency and test-retest reliability, as well as convergent validity with measures of generalised stress and confidence in parenting (Crncec et al. 2008).
- 6) Parent-child bond. This will be assessed using the Mother Object Relations Scale Short Form (MORS-SF). This is a 14-item self-report scale assessing the quality of the parent-child relationship. MORS-SF is recommended by the Royal College of Psychiatrists as a routine outcome measure in perinatal psychiatry. The measure has demonstrated good internal consistency and convergent validity with measures of infant temperament and parental mental state (Oates et al. 2019).
- 7) Child socioemotional development. This will be assessed using the 19-item parent-completed Ages and Stages Social Emotional Questionnaire (version 2) for ages 1 to 3 months (Squires et al. 2015).
- 8) Parental sensitivity. This will be rated by a trained researcher based on video data of parent-child interaction, using the Parent-Infant Interaction Observation Screen. This is an observational coding BOOST-2 Boosting Baby Communication & Play Protocol V1.1 Date 22-06-2021

tool that provides a measure of parental sensitivity based on 3 to 4 minutes of video footage. It has demonstrated good internal consistency and inter-rater reliability, and convergent validity with other measures of parent-child interaction (Svanberg et al. 2013).

6.5 Study assessments

6.5.1 Post-intervention assessment

This will occur at 5 months after baseline, at which point participants should have completed the intervention. The following measures will be used:

- 1) Parental emotion dysregulation. This will be assessed using the Difficulties in Emotion Regulation Scale (DERS-16) (Gratz and Roemer, 2004, Bjureberg et al., 2016), a 16-item self-report measure. The measure
- demonstrates high internal consistency, good test-retest reliability, and adequate construct and predictive validity (Gratz and Roemer, 2004, Bjureberg et al., 2016).
- 2) Parenting Stress. This will be measured using the Parental Stress Scale. This is an 18 item self-report scale assessing positive and negative experiences of parenthood. The measure has demonstrated good internal consistency and test-retest reliability, as well as convergent validity with measures of emotional distress and parenting satisfaction (Berry & Jones 1995).
- 3) Parental self-efficacy. This will be measured using the Karitane Parenting Confidence Scale. This is a 15- item self-report scale assessing mothers' perceived self-efficacy in caring for their child. The measure has demonstrated good internal consistency and test-retest reliability, as well as convergent validity with measures of generalised stress and confidence in parenting (Crncec et al. 2008).
- 4) Parent-child bond. This will be assessed using the Mother Object Relations Scale Short Form (MORS-SF). This is a 14-item self-report scale assessing the quality of the parent-child relationship. MORS-SF is recommended by the Royal College of Psychiatrists as a routine outcome measure in perinatal psychiatry. The measure has demonstrated good internal consistency and convergent validity with measures of infant temperament and parental mental state (Oates et al. 2019).
- 5) Child socioemotional development. This will be assessed using the 22-item parent-completed Ages and Stages Social Emotional Questionnaire (version 2) for ages 3 to 8 months (Squires et al. 2015).
- 6) Parental sensitivity. This will be rated by a trained researcher based on video data of parent-child interaction, using the Parent-Infant Interaction Observation Screen. This is an observational coding tool that provides a measure of parental sensitivity based on 3 to 4 minutes of video footage. It has demonstrated good internal consistency and inter-rater reliability, and convergent validity with other measures of parent-child interaction (Svanberg et al. 2013).
- 7) Therapeutic alliance. This will be assessed using the Helping Alliance Questionnaire-II (HAQ-II). This is a 17-item self-report scale, with a service-user completed version and a clinician-completed version, assessing the quality of the therapeutic alliance between the service-user and the clinician. The measure has demonstrated good internal consistency and convergent validity with other measures of the alliance (Luborsky et al. 1996).

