	Email [contact]			
	[contact]			

STUDY SUMMARY

It may be useful to include a brief synopsis of the trial for quick reference. Complete information and, if required, add additional rows.

Study Title	Boosting Baby Communication and Play: Optimising Video Feedback for Perinatal Mental Health			
Internal ref. no. (or short title)	BOOST-2: Boosting Baby Communication and Play			
Study Design	Case series			
Participants	The study will include women who:			
	 Are using community perinatal mental health services Are a primary caregiver of a child aged 2 to 3 months 			
	3) Are capable of giving ir	formed consent		
	4) Are aged 16 to 65			
Planned Sample Size	N = 10	N = 10		
Treatment duration	3 to 5 months	3 to 5 months		
Follow up duration	5 months	5 months		
Planned Study Period	01/07/2021 to 31/03/2021			
	Objectives	Outcome Measures		
Primary	To evaluate the feasibility and acceptability of the adapted Video feedback intervention for Positive Parenting (VIPP), for mothers using perinatal mental health services and their 2 to 6 month old infants	1) % of trained clinicians implementing at least 1 VIPP intervention case 2) % of mothers invited to participate who give informed consent to do so 3) % of mothers initiating and completing the VIPP intervention 4) mother and clinician ratings of the therapeutic alliance during VIPP 5) participants' own accounts of their experiences of the feasibility and acceptability of the intervention, assessed using qualitative interviews		

BOOST-2 Boosting Baby Communication & Play

Secondary	To establish pre-post effect	1) Parental Stress Scale
	sizes and confidence	2) Parent Expectations
	intervals on outcomes	Survey
	relating to parenting stress,	3) Mother Object Relations
	parental self-efficacy, the	Scale – Short Form
	parent-child bond, parent-	(MORS-SF)
	child interaction and	4) Parent-Infant Interaction
	emotional dysregulation	Observation Screen
		5) Difficulties in Emotion
		Regulation Scale

FUNDING AND SUPPORT IN KIND

FUNDER(S) (Names and contact details of ALL organisations providing funding and/or support in kind for this trial)	FINANCIAL AND NON FINANCIALSUPPORT GIVEN
Barts Charity: [name]	£42,637.34
Central and North West London NHS Foundation Trust: [name]	£ 9,998.00

ROLE OF STUDY SPONSOR AND FUNDER

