3.1 Intervention

Six 90 minute Baby Communication and Play sessions using the Video-feedback Intervention to promote Positive Parenting (VIPP), to be delivered every two weeks. VIPP is a manualised intervention which provides parenting feedback based on videoed interactions between parent and child. VIPP helps parents to recognise, understand and respond sensitively to their child's behaviour. Positive and non-judgemental feedback is used to focus on parents' strengths and help them feel confident in their parenting. As in our previous BOOST research study, based on feedback from our expert-by-experience co-investigator [name], and our PPI group of parents with a diagnosis of a personality disorder, we have incorporated additional elements into the training for clinicians delivering the intervention, to help them focus on building trust and addressing parents' concerns around feeling judged. For this new project, as detailed above, we have adapted the intervention protocol to include activities that are appropriate for younger babies, and to include brief psychoeducation materials on helpful emotion regulation strategies. We have gained management support for perinatal mental-health clinicians to train in and deliver the intervention. Sessions will primarily be delivered using Zoom video conferencing software with participants situated in their homes and clinicians situated in their clinic. The therapists will receive supervision on every session by certified VIPP supervisors.

BOOST-2 Boosting Baby Communication & Play

Participants receiving the intervention will also access treatment as usual from perinatal, adult mental health and/or social services during the trial.

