5.1 Inclusion criteria for service-user participants

The study will include women (people assigned female at birth and/or currently identifying as female) who:

- Are using community perinatal mental health services
- Are a primary caregiver of a child aged 2-3 months at intervention initiation
- Are capable of giving informed consent
- Are aged 16 to 65

5.2 **Exclusion criteria for service-user participants**

The study will exclude:

- Families where a sibling or co-parent is participating in the trial
- Families in which the eligible child has a clinical diagnosis of a learning difficulty, developmental disorder or sensory impairment.
- Families in which the eligible parent has English language or learning difficulties that are sufficiently severe to prevent them completing study measures even with assistance.

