6.5.2 Qualitative interview

Additionally, participants will be asked to take part in a qualitative interview about their experiences of the intervention and of the study. This will occur at 5 months after baseline, at which point participants should have completed the intervention. Interviews will be guided by a semi-structured topic guide, which will include some predetermined questions but will also be open-ended and flexible in order to allow for the emergence of new themes during the interviews. We will investigate the acceptability of the modified VIPP intervention through addressing themes such as parents' expectations and experiences of the intervention, its appropriateness for their child's stage of development, what they found helpful or less helpful, and potential changes that could be made to improve their overall experience of the intervention. We will explore their opinions on the acceptability and feasibility of virtual intervention delivery. The interview will be designed to last approximately 30-60 minutes and will be audio tape recorded for subsequent transcription.

Clinicians delivering the intervention will also be interviewed after intervention delivery, to explore their experiences of benefits, challenges, feasibility, acceptability and suitability for babies aged 2 to 6 months.

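### The post-intervention visit is fixed at 5 months after baseline, but the stated treatment duration runs up to 5 months and the start is not tied to baseline, so some mothers may be assessed mid-treatment and analysed as post-intervention

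*Protocol*

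**What the plan says.** Four provisions of the protocol bear on this point.

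- **Visit.** Section 6.5.1, on the post-intervention assessment: "This will occur at 5 months after baseline, at which point participants should have completed the intervention". Section 6.5.2 repeats this timing for the mothers' interview.
- **Duration.** The study summary gives treatment as 3 to 5 months and follow-up as 5 months. Section 3.1 describes six sessions "to be delivered every two weeks".
- **Start.** Section 5.1 sets the child's age at the first session: "Are a primary caregiver of a child aged 2-3 months at intervention initiation". The summary gives the same age range without saying when it applies. Section 6.4 does not place baseline relative to session 1. Its child questionnaire is the "Ages and Stages Social Emotional Questionnaire (version 2) for ages 1 to 3 months", so that form can be used before the child is old enough to start.
- **Use.** Section 7.3 computes effect sizes from before to after the intervention, uses them to size a definitive trial, and compares them with the earlier BOOST trial to look for dilution. Section 7.4 analyses every recruited mother, whatever number of sessions she received.

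**The concern.** The visit clock starts at baseline and the treatment clock starts at session 1. The longest stated treatment duration equals the whole interval from baseline to the visit, which leaves no room for any delay in starting. The expectation in Section 6.5.1 that mothers are finished by the visit therefore conflicts with part of the duration range in the summary.

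A mother still in treatment at 5 months would give a part-treatment measurement under a post-intervention label. Sections 3 and 7.1 provide for replacing mothers who discontinue or are lost, but a mother still attending is neither.

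The consequences fall on the pre-post effect sizes, the alliance questionnaire (collected at this visit), the interview, and the Section 7.3 rule that no increase in the percentage rated sensitive is potential evidence of dilution. An unfinished course would probably lower the observed change, though not certainly, and the adaptation could be blamed for what the timing caused.

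**Working it through.** **Inputs.** Visit at 5 months after baseline (Sections 6.5.1, 6.5.2); duration 3 to 5 months (summary); six fortnightly sessions (Section 3.1). The protocol does not state the gap g from baseline to session 1, so a range is assumed below. One month is taken as 365.25/12 = 30.44 days, so 5 months = 5 × 30.44 / 7 = 21.7 weeks.

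**Formula.** Treatment ends g + span after baseline. It is complete by the visit only if g ≤ 5 months − span.

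| Course | Span, weeks | Span, months | Longest gap that allows completion |
|---|---|---|---|
| Six sessions, five 2-week intervals | 10 | 2.3 | 2.7 months (11.7 weeks) |
| Six 2-week blocks | 12 | 2.8 | 2.2 months (9.7 weeks) |
| Summary, 3 months | 13.0 | 3.0 | 2.0 months (8.7 weeks) |
| Summary, 4 months | 17.4 | 4.0 | 1.0 month (4.3 weeks) |
| Summary, 5 months | 21.7 | 5.0 | 0 |

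**The same relation by assumed gap.** The longest course that still finishes by the visit is 5.0 months at g = 0, 4.5 months at 2 weeks, 4.1 months at 4 weeks and 3.2 months at 8 weeks.

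**Duration against schedule.** Six fortnightly sessions span 2.3 to 2.8 months, below the lower end of the summary's range. Spreading six sessions over 5 months needs a mean interval of 21.7 / 5 = 4.3 weeks, about twice the stated two weeks. A 5-month course begun at 2 to 3 months of age ends at 7 to 8 months, whereas Section 6.5.2 asks clinicians about "suitability for babies aged 2 to 6 months". These passages do not agree with one another.

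**Weight of one mother.** If 10 mothers have paired sensitivity ratings, one mother is 1/10 = 10 percentage points. The BOOST reference in Section 7.3 is a 15-point rise (Section 1: 35% to 50%). With additional recruits the share per mother would be smaller.

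**The case against.** The strongest reply is that the fortnightly schedule leaves ample room. Six sessions take 10 to 12 weeks, leaving 9.7 to 11.7 weeks for a late start or missed sessions. This stands. It means that mid-treatment assessment is possible, not certain.

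A reader might go further and infer that even fortnightly courses overrun. With baseline at 1.0 month of age and a start at 3.9 months, the last session falls 3.9 + 2.3 − 1.0 = 5.2 months after baseline. The documents do not support using this as a typical case. It takes the entry age from a questionnaire's age band, which is not an eligibility criterion, and it stretches the 2-to-3-month start to its limit. A start at 3.0 months gives 2.0 + 2.3 = 4.3 months. If the summary's age range applies at baseline, the gap is at most 1.9 months, and even a 3-month course ends at 4.9 months.

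A reader might also infer that the completion percentage is lowered. Section 7.3 sets no time limit for completing and does not tie that figure to the visit, so a mother who finishes later can still count.

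A fixed visit is a legitimate choice. It matches the 5-month follow-up in BOOST, which is the comparator for the dilution check, and Section 7.4 includes partly treated mothers on purpose. This is a reason to keep 5 months as the nominal time. It does not make a mid-treatment value a post-intervention one, which is how Sections 6.5.1 and 7.3 treat it.

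Finally, visit windows and rules for off-schedule data are often left to an analysis plan, and their absence is not the point here. The visit anchor and the treatment duration are protocol provisions, they conflict, and an analysis plan cannot recover a measurement taken too early.

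**Conclusion.** The point holds in a limited form. At the upper end of the stated duration, any delay in starting puts the visit before the last session. At 4 months a delay of more than 1 month does so, and at 3 months a delay of more than 2 months. On the fortnightly schedule most mothers would finish in time. The protocol gives neither the gap nor the spread of course lengths, so the number affected cannot be estimated and may be none.

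The effect sizes, the dilution check, the alliance ratings and the mothers' interview are exposed; the completion percentage is not necessarily so. Tying the age criterion to session 1 is not an error in itself. It matters only because baseline is not tied to session 1 as well. The point is worth correcting because the series is small and its results feed the design of the next trial, but it does not undermine the study.

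**What to change.** 1. The sponsor should reconcile the 3-to-5-month duration, the six fortnightly sessions, the 2-to-6-month target age and the 5-month visit. Which of them should change is for the sponsor to decide.
2. In Section 6.4, take the baseline measures within a short stated window before session 1, and repeat them if the start slips. A 14-day window, for example, would let any course up to 4.5 months finish by the visit. State which set of measures starts the 5-month clock.
3. In Sections 6.5.1 and 6.5.2, keep the visit and interview at 5 months. For a mother still in treatment, hold them after her last session or documented discontinuation, within a bounded window.
4. Record the number of sessions completed at assessment. Report the pre-post and dilution results with and without mothers who had sessions outstanding.

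**Cost.** A protocol amendment, an occasional repeat of a 20-minute questionnaire and a 10-minute video, and a slightly variable follow-up interval. With a single group this creates no imbalance between arms, but it loosens the comparison with BOOST a little.

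Two limits constrain the extension. The follow-up child form is the "Ages and Stages Social Emotional Questionnaire (version 2) for ages 3 to 8 months", and a child aged 3 months at baseline is already 3 + 5 = 8 months old at the visit. Mothers recruited in October 2021 reach 5 months in March 2022, which is the closing month if the printed end date of 31/03/2021 is meant to read 2022 (an assumption). Late visits could therefore need a short study extension.
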